12.3 Clinical Laboratory Adverse Events

The investigator is responsible for reviewing the results of all laboratory tests as they become available and determining whether an abnormal value in an individual subject is a clinically significant change from the subject's baseline value(s). The investigator may repeat the laboratory test or request additional tests to verify the results of the original laboratory tests. In general, abnormal laboratory findings without clinical significance (based on the investigator's judgment) are not to be recorded as AEs. However, laboratory value changes that require treatment or adjustment in current therapy are to be considered AEs. When applicable, clinical sequelae (not the laboratory abnormality) are to be recorded as the AE.

Equillium, Inc.	Clinical Study Protocol No. EQ001-19-002	Page 76 of 110

12.4 Serious Adverse Events

A serious adverse event (SAE) is defined as any AE occurring at any dose that results in any of the following outcomes:

- Death
- Life-threatening AE (Note: A life-threatening AE is one that, in the view of the investigator places the subject at immediate risk of death from the reaction as it occurred)
- Hospitalization or prolongation of existing hospitalization
- A persistent or significant disability/incapacity
- A congenital anomaly/birth defect.

Important medical events that may not result in death, be life threatening, or require hospitalization may be considered an SAE when, based upon appropriate medical judgment, they may jeopardize the subject and may require medical or surgical intervention to prevent one of the outcomes listed in this definition. Examples of such medical events include blood dyscrasias or convulsions that do not result in subject hospitalization, or the development of drug dependency or drug abuse.

All SAEs, regardless of cause(s) or causal relationship to study drug, must be reported within 24 hours to the study Sponsor and/or designee. If an SAE occurs outside the reporting window of the subject's follow-up or ET visits and is considered related to study treatment, it must be reported to the Sponsor within 24 hours of the site's awareness.

12.5 Reporting Adverse Events

12.5.1 Reporting Procedures for Nonserious Adverse Events

The investigator is responsible for ensuring that all AEs observed by the investigator or designee or reported by the subject are reported using the AE eCRF.

The investigator will assign the following AE attributes:

- AE diagnosis or syndrome(s), if known (if not known, signs or symptoms)
- Dates of onset and resolution (if resolved)
- Severity
- Causality relationship to study drug or study-related procedures
- Action taken
- Outcome

Equillium, Inc.	Clinical Study Protocol No. EQ001-19-002	Page 77 of 110	

Follow-up of nonserious AEs will continue through the last day on the study and/or until a definitive outcome (e.g., resolved, resolved with sequelae, lost to follow-up) is achieved.

When a subject is withdrawn from the study because of a nonserious AE, the Sponsor and/or designee must be notified by email or phone within 48 hours.

12.5.2 Reporting Procedures for Serious Adverse Events

The investigator is responsible for ensuring that all SAEs observed by the investigator or reported by the subject are promptly assessed and reported to the Sponsor and/or designee. The investigator must assess the causality relationship of the SAE to study drug or any study-related procedure.

The procedures for reporting SAEs are as follows:

- Within 24 hours of the investigator's knowledge of the event, enter data into the AE/SAE eCRF. If the EDC is not available, the paper SAE Report Form may be used, but all data must be entered into the EDC once the EDC is available.
- Additional contact numbers and AE/SAE reporting instructions will be provided in the eCRF Completion Guidelines.
- For fatal or life-threatening events and all SAEs, also email and/or fax redacted copies of
 hospital records, autopsy reports, and other documents, when requested and applicable.
 Transmission of such documents should occur with personal subject details de-identified
 (redacted), without losing the traceability of a document to the subject identifiers. Entry
 of the initial report of the event into EDC should not be delayed in order to include these
 additional documents.
- The Sponsor and/or designee may request additional information from the investigator to ensure the timely completion of accurate safety reports.

The investigator must take all necessary therapeutic measures for resolution of the SAE. Any medications or therapies necessary for treatment of the SAE must be recorded in the event description section of the SAE form and the concomitant medication eCRF.

[figure not shown]
Follow-up of SAEs will continue through the last day on the study and/or until a definitive outcome (e.g., resolved, resolved with sequelae, lost to follow-up, fatal) is achieved.

[figure not shown]
While pregnancy is not considered an AE, all cases of fetal drug exposure via a maternal parent as study subject or pregnancy of a partner of a male study subject that occurs during the study or within 130 days after the last dose of study drug will be reported immediately to the Sponsor or its designee. Information related to the pregnancy must be documented on a Pregnancy Confirmation and Outcome Form, provided by the Sponsor or its designee, and the pregnancy should be followed until a definitive outcome has been determined.

Equillium, Inc. Clinical Study Protocol No. EQ001-19-002 Page 78 of 110

The Sponsor or its designee will report SAEs as required to regulatory authorities and investigators in compliance with all reporting requirements, according to local regulations and ICH Good Clinical Practice (GCP).

The investigator will notify the appropriate IRB/IEC of SAEs occurring at the study site and other AE reports received from the Sponsor, in accordance with local requirements. The investigator or designee at each study site is responsible for submitting safety reports (initial and follow-up) and other safety information to the IRB/IEC and/or other applicable regulatory authorities for retaining a copy in the study files.

13.1 General Considerations

Data will be summarized using descriptive statistics (n, mean, median, standard deviation, minimum, maximum) for continuous variables and frequencies and percentages for discrete variables. All data summaries will be displayed by cohort. Data may also be pooled across cohorts. Baseline values of variables are considered the last available non-missing value prior to receiving any study drug unless otherwise specified. By-subject listings of the data will also be provided. All data summaries and listings will be produced using the SAS® software, version 9.3 or higher.

13.3 Analysis Populations

13.3.1 Safety Population

The *safety population* consists of all subjects who receive any study drug.

13.3.2 Pharmacokinetic Analysis Population

The *pharmacokinetics population* includes those subjects in the safety population who have at least one measurable post-EQ001 exposure serum concentration.

13.3.4 Efficacy Population

Subjects in the safety population who have at least 1 post-treatment assessment for a marker of clinical activity will be included in the efficacy population.

13.4 Subject Disposition

Subject disposition data will be summarized and will include the number and percent of enrolled subjects; number and percent of subjects initiating and completing treatment; and number and percent of subjects discontinuing treatment and discontinuing the study, further broken down by

Equillium, Inc.	Clinical Study Protocol No. EQ001-19-002	Page 80 of 110	
_			

the reasons for discontinuation. Subject enrollment will also be summarized by study site. A summary of major protocol deviations will be tabulated for each cohort.

13.5 Demographics and Baseline Characteristics

Demographics and other baseline characteristics will be summarized for the subjects in the safety population. Demographic data will include age, gender, race, and ethnicity. Baseline characteristics data will include (but not be limited to) renal function, proteinuria (UPCR), complement, and autoantibody titers. Medical history data will include (but not be limited to) time from diagnosis of SLE to Screening, prior and current medications used for SLE, including use of biologic therapy for SLE.

13.6 Statistical Analysis of Pharmacokinetic Variables

Serum concentrations will be listed and summarized for each EQ001 dose using descriptive statistics for each cohort.

13.7 Safety Analyses

All safety data summaries will use the safety population.

The number and percent of Type A subjects experiencing any DLTs will be presented by cohort. A listing of DLTs will also be provided.

Adverse events (including DLTs) will be coded using the Medical Dictionary for Regulatory Activities (v 20.1, or higher version) and will be graded by the investigator using the NCI CTCAE v 5.0. Subject incidence of TEAEs, TESAEs, TEAEs leading to treatment discontinuation, AESIs, and TEAEs with an outcome of death will be summarized by SOC and preferred term. Adverse events will also be further summarized by worst CTCAE severity grade and relationship to study drug. In addition, AESIs as described in Section 12.6 will also be summarized by SOC, preferred term, and worst severity grade.

Clinical laboratory data will be summarized descriptively, these summaries will include observed values at collection timepoints and their changes from baseline. All laboratory parameters that can be graded using the CTCAE v 5.0 will be graded. For selected parameters, the following summaries may be produced:

- Worst post-baseline severity grade
- Shift summary of baseline grade to worst post-baseline severity grade.

Safety evaluations may also include changes in the subject's vital signs and ECG findings.

Equillium, Inc.	Clinical Study Protocol No. EQ001-19-002	Page 81 of 110
13.9 Efficacy Ana	llyses	
subject receives new i	will use the Efficacy population. Handling of efficacy mmunosuppressive or other treatments for LN or has e described in the Statistical Analysis Plan.	
Analyses will be perfo	ormed by dose and with all doses combined.	
13.9.1 Lupus Nep	hritis Subjects (Type B Cohort)	
13.9.1.1 Proteinu	ria	
spot collections to FU 95% CI for the fold ch will also be described	Fold change from baseline in UPCR from a 24-hour urant 1 and to FU2 will be summarized descriptively, along nange. The geometric mean fold change from baseline. The proportion of subjects with a $> 30\%$ and $> 50\%$ 500 mg/g at FU1 and FU2 will be described, along with the summarized described.	with their 2-sided over time by visit decline in UPCR and
-	nse of UPCR with response defined as a decrease of > from baseline, and a decrease to a level < 500 mg/g with er method.	

13.9.1.2 Serologic Markers Associated with Active LN (C3, C4, anti-dsDNA)

The mean change from baseline in C3, C4, and anti-dsDNA to FU1 and FU2 will be summarized, along with their 2-sided 95% CI for the change. The mean change from baseline over time by visit will also be described.

Equillium, Inc.	Clinical Study Protocol No. EQ001-19-002	Page 82 of 110
-----------------	--	----------------

13.9.1.3 eGFR

The change from baseline in eGFR (mean of all Screening and Day 1 values) will be summarized by time point. The proportion of subjects with a change from baseline to FU1 and FU2 of < 20%, < 30%, and < 40% will be summarized along with their 2-sided 95% CI.

13.9.1.4 Glucocorticoid Dose

The mean change from baseline in the daily prednisone equivalent dose during Screening to the mean daily prednisone dose during the period from FU1 to FU2 will be summarized along with the 2-sided 95% CI. The proportion of subjects (with the 2-sided 95% CI) who had a prednisone dose equivalent < 10.0 mg, < 7.5 mg and < 5.0 mg at FU1 and FU2 will be summarized. This analysis will also be performed for FU3 and FU4.

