Equillium, Inc. Clinical Study Protocol No. EQ001-19-002 Page 12 of 110

The MTD determination will be made based only on Type A Cohorts. Dose escalation is allowed to proceed if no predefined stopping criteria are met and the DRC recommends that it is safe to proceed.

Type B

Up to approximately 20 subjects will be enrolled and dosed in the Type B Cohort. Subjects will receive a total of 13 doses of EQ001 1.6 mg/kg administered SC every 2 weeks over 24 weeks. All subjects must be on a stable dose of mycophenolate mofetil (MMF) or mycophenolic acid (MPA) for the duration of the study. Subjects that require induction treatment with pulse steroid treatment of methylprednisolone ≥500 mg or equivalent will undergo a rapid steroid taper with a 20% reduction per week. The targeted goal is to reach a prednisone dose of 10 mg or less per day by Week 10.

The study will be conducted in 3 defined periods, described below:

- 1. Screening Period
 - a. **Type A Cohorts:** The Screening Period for Cohort A subjects will be up to 4 weeks in duration, starting with the first screening procedure in the Schedule of Events (SOE; excluding the informed consent), and completed prior to Study Day 1 (Section 5.2)
 - b. **Type B Cohort:** The Screening Period for Cohort B subjects will be up to 6 weeks in duration (excluding the informed consent) and completed prior to Study Day 1 and may be completed over the course of multiple clinic visits. (Section 5.3).
- 2. Treatment Period
 - a. **Type A Cohorts**: The Treatment Period for Cohort A subjects will be 4 weeks in duration, beginning on Day 1 with the first study drug dose. During the Treatment Period, 2 doses of study drug will be

[figure not shown]
- administered subcutaneously (SC), 1 dose each on Days 1 and 15. Subjects will return to the study site for follow-up evaluations according to the SOE (Section 5.2).
- b. **Type B Cohort**: The Treatment Period for Cohort B subjects will be 24 weeks in duration, beginning on Day 1 with the first study drug dose. During the Treatment Period, 13 doses of study drug will be administered SC, 1 dose each on Days 1, 15, 29, 43, 57, 71, 85, 99, 113, 127, 141, 155, and 169. Subjects will return to the study site for follow-up evaluations according to the SOE (Section 5.3 and Section 5.4).
- 3. Follow-up Period
 - a. **Type A Cohorts**: The Follow-up Period for Cohort A subjects will end approximately 6 weeks after the last dose of study drug (Section 5.2)

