- 6. (All Regions except Asia-Pacific [APAC]) All subjects must be on MMF/MPA 2 to 3 g/day. For subjects that require induction treatment due to newly diagnosed LN or relapsing/flaring disease, subjects can have pulse systemic corticosteroids administered as part of their induction treatment.
 - (APAC) Requires induction treatment due to newly diagnosed LN or relapsing/flaring disease. Subjects need to be on MMF/MPA (2 to 3 g/day) and pulse systemic corticosteroids as part of their induction treatment. The MMF/MPA and pulse systemic corticosteroids can be started within 12 weeks prior to Day 1 or on Day 1.
- 7. Subjects that require induction treatment must receive at least 2 consecutive days of pulse systemic corticosteroids of methylprednisolone (≥500 mg) or equivalent and be able to receive it 12 weeks prior to Day 1 or start on Days 1 and 2; all induction subjects must be able to undergo a taper of systemic corticosteroids during the first 10 weeks of treatment.
- 8. Within 6 weeks of Day 1 has adequate hematologic function as defined by
 - a. ANC $> 1.5 \times 10^9/L$
 - b. ALC $\geq 1.0 \times 10^9/L$
 - c. Platelet count $> 75 \times 10^9/L$
 - d. Hemoglobin > 8.5 g/dL
- 9. Blood pressure ≤ 170/95 mm Hg without recent clinically significant changes per the investigator
- 10. The investigator considers the protocol-recommended steroid tapering schedule to be clinically appropriate for the subject based on the subject's current status and history
- 11. Has documented elevation of ANAs in the past or currently
- 12. The dose of MMF/MPA and other SLE drug treatments (other than glucocorticoids) are expected to remain stable during the study
- 13. Restricted SLE treatments (e.g., other immunosuppressive medications, antimalarials, ACE inhibitors, and angiotensin receptor blockers) are stable and/or washed out at Screening
- 14. Most recent eGFR ≥ 40 mL/min/1.73m² during Screening
- 15. No recent clinically significant changes in eGFR (increases or decreases) per the investigator
- 16. If the subject is a female of childbearing potential, she must be willing to practice complete abstinence, or she and any male partner are required to simultaneously use 2 effective contraceptive methods, from the following list of 5 methods below throughout the study and for 130 days after the last dose of study drug:
 - A barrier (condoms, diaphragm or cervical cap) with or without spermicide;
 - A second, different barrier method (condoms, diaphragm or cervical cap);

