10.8.2.1 Glucocorticoids

[figure not shown]
In subjects in the Type A cohorts, the dose of glucocorticoids must be kept stable during the study

[figure not shown]
Subjects in the Type B Cohort should be on a stable dose of MMF or MPA for the duration of the study. For subjects that are undergoing induction treatment, they may require additional pulse steroid treatment and receive methylprednisolone ≥500 mg or equivalent within 12 weeks prior to starting study treatment or receive a dose start on Day 1 and Day 2 and then undergo a rapid oral corticosteroid taper, which will be reduced by 20% per week targeting to reach prednisone of approximately <10 mg per day by Week 10. Prednisone or equivalent can be maintained at 7.5 mg per day for the duration of the study

[figure not shown]
Investigators will adhere to the protocol steroid taper schedule unless a safety concern (including

[figure not shown]
Equillium, Inc.	Clinical Study Protocol No. EQ001-19-002	Page 62 of 110

concern related to insufficient response) necessitates departures from the schedule. Such planned departures must be discussed with the Medical Monitor, preferably in advance of the change in medication.

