8.1.3 Change from Baseline in eGFR to FU1 and FU2

This secondary endpoint pertains to Type B cohort subjects only.

The change from baseline in eGFR (baseline value is defined as the mean of Screening and Day 1 values) will be descriptively summarized by visit with central and local versions combined.

The proportion of subjects with a percent decline in eGFR from baseline to FU2 of >=20%, >=30% and >=40% will be summarized along with their 2-sided Clopper–Pearson 95% CIs. In addition, these proportions will also be summarized for all visits.

8.1.4 Change from Baseline in Daily Prednisone Dose and Cumulative Prednisone Dose Through FU1 and Through FU2

This secondary endpoint pertains to Type B subjects only.

Mean daily systemic prednisone equivalent steroid use (mg/day) and change from baseline in Type B subjects will be summarized descriptively by study windows

The proportion of subjects (with the 2-sided 95% Clopper-Pearson CI) with a prednisone daily dose equivalent < 10.0 mg/day, < 7.5 mg/day and < 5.0 mg/day

will be summarized.

Cumulative prednisone dose is computed as the total dose taken during the analysis period (Day 1 through a certain analysis visit). The cumulative prednisone dose will be summarized descriptively.

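### For pulsed Type B subjects, the change in prednisone dose from Screening and the cumulative dose from Day 1 depend on when the induction pulse and early taper fell

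*Protocol*

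**What the plan says.** **Baseline.** Protocol 13.1 sets a default: "Baseline values of variables are considered the last available non-missing value prior to receiving any study drug unless otherwise specified". Protocol 13.9.1.4 specifies otherwise for steroids and summarises "The mean change from baseline in the daily prednisone equivalent dose during Screening to the mean daily prednisone dose during the period from FU1 to" visit FU2, with a 95% CI.

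**SAP.** Section 8.1.4 calls this a secondary endpoint for Type B only. It states: "Mean daily systemic prednisone equivalent steroid use (mg/day) and change from baseline in Type B subjects will be summarized descriptively by study windows". It also states: "Cumulative prednisone dose is computed as the total dose taken during the analysis period (Day 1 through a certain analysis visit". The visible text has no rule on IV pulses and does not repeat the Screening baseline.

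**Pulse.** Under Protocol 9.1.2, criterion 7, subjects who need induction "must receive at least 2 consecutive days of pulse systemic corticosteroids of methylprednisolone (≥500 mg) or equivalent". On timing, Protocol 10.8.2.1 lets them "receive methylprednisolone ≥500 mg or equivalent within 12 weeks prior to starting study treatment or receive a dose start on Day 1 and Day 2". An oral taper of 20% per week follows, and 7.5 mg/day may then be maintained. Outside the Asia-Pacific region, subjects who do not need induction may enter without a pulse.

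**Screening length.** The Protocol synopsis gives Type B up to 6 weeks. SAP 3.2 describes Screening as the 12 weeks before study treatment.

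**Week 10 target.** The synopsis says: "The targeted goal is to reach a prednisone dose of 10 mg or less per day by Week 10". Protocol 10.8.2.1 aims for approximately less than 10 mg.

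**The concern.** The baseline window ends where the cumulative window begins, and the pulse may fall on either side of that boundary. A pulse during Screening raises the baseline, together with the high oral doses that follow it. A pulse on Days 1-2 leaves the baseline untouched and enters the cumulative sum. A pulse 6 to 12 weeks before Day 1 is out of the cumulative sum, and whether it enters the baseline depends on which Screening length applies.

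Two subjects on the same steroid course, ending on the same dose, can therefore report very different reductions and very different exposure. In a single arm of about 20, the mean change and its CI would partly describe the mix of induction dates and a taper scheduled by the protocol. A reader would take them as steroid sparing.

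**Working it through.** The documents give no expected value for this endpoint, so there is no figure to reproduce. I built a daily dose path and moved only the pulse date.

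**From the documents:** two pulse days of 500 mg methylprednisolone (the minimum), oral dose multiplied by 0.8 each week, 7.5 mg/day maintained, Screening of 42 or 84 days, cumulative dose from Day 1.

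**Assumed:** oral dose o before the pulse, 0 to 20 mg/day; oral start S = 60 mg/day the day after the pulse ends; end dose M = 7.5 mg/day; conversion factor 1.25, so the pulse equals 1,250 mg prednisone; FU1 and FU2 on Days 183 and 197. S = 60 fits the stated target: 60 x 0.8^9 = 8.1 mg/day in the tenth week. The taper is over long before FU1, so the FU dates affect only the cumulative dose, by 7.5 mg per day.

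**Formulas.** Change = M - (mean daily dose over Screening). Cumulative = sum of doses from Day 1 to FU2.

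**Pulse on Day 1, o = 5.** Baseline 5.0; change 7.5 - 5.0 = +2.5. Ten taper weeks sum to 7 x 60 x (1 - 0.8^10)/0.2 = 1,874.5 mg. Cumulative = 1,250 + 1,874.5 + 125 x 7.5 = 4,062 mg.

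**Pulse 14 days before Day 1, o = 5, 42-day Screening.** Baseline = (28 x 5 + 1,250 + 7 x 60 + 5 x 48)/42 = 2,050/42 = 48.8; change = -41.3. The 12 taper days before Day 1 used 660 mg, so cumulative = (1,874.5 - 660) + 139 x 7.5 = 2,257 mg.

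All rows below use o = 5. Changes are in mg/day.

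| Pulse | Change, 42-day Screening | Change, 84-day Screening | Change, last pre-dose value | Change, 42-day, IV pulse excluded | Cumulative from Day 1 (mg) |
|---|---|---|---|---|---|
| Day 1 | +2.5 | +2.5 | +2.5 | +2.5 | 4,062 |
| 14 days before | -41.3 | -19.4 | -40.5 | -11.5 | 2,257 |
| 42 days before | -58.2 | -27.9 | -12.2 | -28.5 | 1,617 |
| 70 days before | -8.7 | -30.3 | -0.6 | -8.7 | 1,479 |

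None of these baseline rules removes the dependence. Excluding the IV pulse is not enough, because the oral taper stays in the baseline. With the pre-pulse dose as baseline and accumulation over 197 days from the pulse date, every row becomes +2.5 mg/day and 4,062 mg.

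**Ranges.**
- Day 1 pulse: change = M - o, which is +7.5, +2.5, -2.5 and -12.5 for o = 0, 5, 10 and 20. With M = 10 it runs from +10 to -10.
- Pulse 14 to 42 days before, 42-day Screening, M = 7.5, S of 30 or 60, factor 1.0 or 1.25: always negative, about -24 to -58.
- Pulse 84 days before, 42-day Screening, S = 60: -3.3, so the smallest effect is near zero.
- The minimum pulse alone adds 1,000/42 = 23.8 to 1,250/42 = 29.8 mg/day to a 42-day mean, or 11.9 to 14.9 over 84 days.

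**Cohort mean.** Suppose k of 20 subjects are pulsed on Day 1 (change a) and the rest earlier (change -d). The mean is positive when k > 20d/(a + d). For pulses 14 days before with 42-day Screening, o = 5 gives 20 x 41.3/43.8 = 18.9, so 19 of 20 (mean +0.3; with 10 of 20 it is -19.4). At o = 0 it is 20 x 38.0/45.5 = 16.7, so 17. If all the others were pulsed 70 days before (d = 8.7), 16 suffice at o = 5 and 11 at o = 0.

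**The case against.** **The SAP may already settle this.** SAP 6.2 (Key Definitions) is not visible, and 8.1.4 breaks off where windows and visits would stand. Protocol 13.9.1.4 also does not say that the Screening dose is a mean including the pulse. This stands as a limit: nobody can infer that the SAP lacks a pulse rule. A hidden rule that only drops the IV pulse would not be enough, though; one anchored before the pulse would.

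**The Protocol already plans to look at time since pulse.** The synopsis allows subjects to be assessed by time since pulse corticosteroids, split at 12 weeks or by quartiles, and SAP 7.6.3 summarises time since the last induction treatment. Quartiles could help. But the analysis is optional and not tied to this endpoint, and the 12-week cut does not separate Day 1-2 pulses from those in the preceding 12 weeks.

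**Parts of the output do not depend on the baseline.** Mean daily dose by window and the proportions below each cut-off are already planned, and dose from Day 1 is a legitimate measure of on-study exposure. This stands, and it makes the fix mostly a matter of emphasis and stratification.

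**The study is descriptive.** SAP 6.1 plans no hypothesis tests. That lowers the stakes, but a mean change with a CI will still be read as steroid sparing.

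**Stronger readings the documents do not support.** A reader might infer that the endpoint as a whole can reverse sign. Cumulative dose cannot. The change is positive for a subject pulsed on Day 1 only if the pre-pulse dose is below the FU1-FU2 dose; at 10 mg/day before and 7.5 after, only its size varies. A positive cohort mean needs a large share of Day 1 pulses and low prior doses, neither of which the documents state. A reader might also infer that a pulse 6 to 12 weeks before Day 1 is counted nowhere. That follows from the 6-week Screening but not from the SAP's 12-week description. Finally, the strict cut-offs (below 10.0 and below 7.5 mg) exclude subjects exactly at those doses, but that is a choice of presentation, not an error.

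**Conclusion.** The point holds for pulsed induction subjects. On the visible text, both summaries mix steroid use with the calendar position of a planned pulse. With a 60 mg/day oral start, 7.5 mg/day end dose, factor 1.25, prior dose of 0 to 20 mg/day and Screening of 42 or 84 days, one identical course gives:

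- change from baseline of +7.5 to -12.5 mg/day for a Day 1 pulse, against about -9 to -58 for a pulse 14 to 70 days earlier;
- cumulative dose of about 4,060 mg against 1,480 to 2,260 mg.

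The direction of the dependence comes from the documents; its size comes from the assumed doses and dates. Subject-level increases are possible, and a sign flip of the cohort mean is unlikely when earlier pulses fell within a 42-day Screening. Subjects without a pulse are unaffected. Confidence is medium because of the SAP text that is not visible. The change should be made before database lock.

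**What to change.** - Make the daily oral prednisone-equivalent dose at FU1 and FU2 the main steroid result.
- State the steroid baseline window and how IV pulses are handled, and tabulate IV pulses separately.
- Present change from baseline and cumulative dose separately for subjects pulsed before Day 1, pulsed on Days 1-2, and not pulsed.
- Where records allow, add a version with the pre-pulse dose as baseline and accumulation over a fixed period from the pulse date. Excluding the IV pulse alone does not replace this.
- Optionally show the proportions at or below 10 mg and 7.5 mg beside the strict cut-offs.
- Reconcile the Screening length (6 weeks in the Protocol synopsis, 12 weeks in SAP 3.2) and the Week 10 target wording (synopsis and Protocol 10.8.2.1). The inequality sign may have suffered in text extraction, so check the source first.

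**Cost.** SAP wording and a few table rows from dosing records, plus pre-pulse doses where available. The subgroups will be small, and the mean reduction will look smaller once the pulse and early taper no longer inflate the baseline.
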